## **Introduction**

All hospital-acquired infections (HAI) and especially, HAI due to multi-drug resistant (MDR) micro-organisms are, nowadays, one of the most relevant matter of concern because of their clinical and economic consequences [1-2].

Several infection control measures (systematic careful hand hygiene, selective and universal decontamination, etc...) have been investigated for their effect on HAI acquisition rate [3-6]. Chlorhexidine gluconate-based universal decontamination appear to be a promising strategy [8], but other studies didn't support these findings [8].

## **Aims of the study**

### *Main aim:*

Evaluation of the effect of daily bathing with 4% chlorhexidine gluconate (CHG)-containing soap on the incidence of HAI in 2 intensive care units.

### *Secondary aim:*

Evaluation, if possible, of the effect of daily bathing with 4% CHG-containing soap on the incidence of possible and probable ventilator-associated pneumonia (VAP), bloodstream infection (BSI), central-line associated bloodstream infections (CLABSI), urinary tract infections (UTI) and catheter-associated urinary tract infections (CAUTI).

## **Definitions and methods:**

Demographic characteristics and clinical data of patients will be collected using a case report form that was elaborated specifically for this study (attachment 1) .

### *Definitions*

We will take into consideration only the infections arisen at least 48 hours after the admission to the above mentioned wards.

Sepsis is defined as a systemic inflammatory response syndrome (SIRS) with a probable and/or confirmed infection [9].

Specifically, VAP, BSI, CLABSI, UTI e CAUTI are defined according to the National Healthcare Safety Network - Centers for Diseases Control and Prevention definitions [10].

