## **Study design**

Prospective single-blinded randomized case-control study.

Study population: all patients admitted to the Intensive Care Unit (ICU) or to the Post-Cardiosurgical Intensive Care Unit (PC-ICU) of the University Hospital of Perugia will be enrolled.

These patients will be randomized in two arms using a specific software. Patients in the first arm (control arm) will undergo the usual hygiene procedures with standard soap; in the second arm (treatment arm) patients will be bathed with 4% CHG-containing soap (Neoxidina mani 4%), at least 30 ml according to the manufacturer indications (see the attached data sheet). In particular the whole body surface - except for the face - will be i) humidified

[figure not shown]
with water impregnated washcloths, ii) bathed with 4% CHG-impregnated washcloths (at least 30 ml) and, after at least 30 seconds, iii) rinsed with water-impregnated washcloths.

This product is already in use in our hospital to prepare patients before a surgical intervention. We will evaluate and compare the global incidence of sepsis in the two arms and, secondary, incidence of VAP, BSI, CABSI, UTI and CAUTI.

In addition to this, we will collect demographic data of each patients and data about comorbidities, cause of admission and infections occurred during the hospital stay.

This study is single-blind. Physicians that have to collect data, to diagnose infections and to analyse data won't be directly involved in washing procedures and they are not member of the medical staff of ICU and/or TIPOC. Moreover, only nurses that will wash patients by their own hands will know the arm in which the patient is. Both the usual soap and the Neoxidina mani 4% (with chlorhexidine gluconate 4%) have no colour nor other item than can favour their identification.

*Figure 1: Study design*

*Patients enrolment.*

Inclusion criteria: all patients aged  $\geq 18$  years old admitted to ICU or TIPOC.

Exclusion criteria:

- Age  $< 18$  years old;
- patients with burns;
- patients with known allergy to chlorhexidine and/or one of the components of Neoxidina mani 4%;
- patients with toxic epidermal necrolysis o Stevens-Johnson syndrome.
- pregnancy

Data will be collected on specific paper form and, then, analyzed using computerized methods (section "Criteria and data collection methods").

*Relative risk of the procedure and risk/benefit evaluation.*

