### **Sample Size**

Sample size will be between 420 and 1000 patients. Sample size was calculated after a pre-trial evaluation of HAI. We retrospectively measured the pre-trial incidence of HAI at ICU and PC-ICU (patients admitted to ICU and PC-ICU between January, 1st and January, 31st 2015). Twenty patients out of 66 suffered from at least 1 HAI (incidence 30.3%).

By adopting an alpha error tolerance (false-positive risk) equal to 0.05, beta error tolerance (false-negative risk) equal to 0.1, power equal to 0.9, a potential reduction of HAI incidence by 10% and a percentage between 5% and 8% of potential dropouts, we calculated that a sample size of at least 410-420 patients would be required to provide sufficient power to detect significant differences. According to the Italian Law, patients with altered mentation at the admission could be directly enrolled by the physician after a clinical evaluation. At the recovery of consciousness, the patient will receive the specific paper to provide his consent or not.

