## **Patient's consent**

Patients will be informed about the study protocol by an ad hoc chart with which they can provide their consent. For unconscious patients or patients unable to provide their consent, at admission a physician will decide patients' enrolment on the basis of their clinical conditions. These patients will provide their consent as soon as they regain consciousness.

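### Infections are counted from 48 hours after unit admission with no reference to randomisation, so for anyone randomised later than that an infection preceding randomisation would count (minor)

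*Combined protocol and SAP*

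**What the plan says.** **Outcome clock.** Definitions gives one rule: "We will take into consideration only the infections arisen at least 48 hours after the admission to the above mentioned wards". Study design adds that data will be collected on "infections occurred during the hospital stay" and states the main comparison as "We will evaluate and compare the global incidence of sepsis in the two arms". None of these refers to the date of randomisation or of the first bath.

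**Entry.** The inclusion criterion is age 18 or over and "years old admitted to ICU or TIPOC". The five exclusions concern age, burns, allergy, two skin conditions and pregnancy. None concerns time already spent in the unit or an infection already present. On allocation, Study design says "These patients will be randomized in two arms using a specific software", and Data collection adds that it is simple, 1:1 and at patient level. Neither says when.

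**Timing of consent and enrolment.** Patient's consent says "Patients will be informed about the study protocol by an ad hoc chart with which they can provide their consent", without a time. For those unable to consent, the same section says "at admission a physician will decide patients' enrolment on the basis of their clinical conditions". Sample Size puts it more loosely: "patients with altered mentation at the admission could be directly enrolled by the physician after a clinical evaluation". This is the only text that ties enrolment to admission, and it covers only patients who cannot consent.

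**The concern.** The outcome and the allocation run on different clocks. A rule of 48 hours from admission separates infections acquired in the unit from those brought into it. It does not ensure that a counted infection came after allocation. That would follow only if every patient were randomised within 48 hours of admission, which the protocol does not require.

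Two groups could be affected under the written criteria: conscious patients who consent late, and patients already in the unit when recruitment opens. In either group an infection on day 3 before randomisation on day 4 would count as a trial event.

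Such an infection cannot depend on the arm, so it adds about equally to both. The risk ratio moves towards 1 and the test loses power.

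**Working it through.** **1. What the text implies.** Let R be the time from admission to randomisation and T the time from admission to onset of infection.
- Counting rule in Definitions: T ≥ 48 h.
- Counted but before randomisation: 48 h ≤ T < R. This is possible only if R > 48 h.
- Limit on R in the protocol: none.

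The gap is therefore real, and it is confined to patients with R > 48 h.

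**2. Planning inputs.**
- Control risk 20/66 = 30.3% (Sample Size).
- Reduction of 10% (Sample Size), read here as absolute, giving 20.3%. The protocol does not say whether it is absolute or relative.
- Alpha 0.05, power 0.9, dropout 5% to 8% (Sample Size). Two-sided testing is assumed.
- Chi-square test with Yates' correction (Data analysis).
- 420 to 1000 patients, 1:1 (Data collection), so 210 to 500 per arm.

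**3. The plan's own figure.** The usual two-proportion formula is n per arm = [1.96 √(2p̄(1−p̄)) + 1.2816 √(p1(1−p1) + p2(1−p2))]² / (p1−p2)². With p1 = 0.303, p2 = 0.203 and p̄ = 0.253 it gives 396 per arm, 792 in total. With dropout this is 792/0.95 = 834 to 792/0.92 = 861. The stated 410 to 420 is not reproduced as a total. It is close to a per-arm number (396/0.95 = 417). That is a separate matter, but it explains the low starting power at 420 below.

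**4. Dilution.** Let g be the share of control-level events that arose before randomisation and so cannot respond to treatment. The documents give no value for g, so the range is an assumption.

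Treated risk = 0.303 g + 0.203 (1 − g), and the difference from control = 0.10 (1 − g).

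Power is exact: binomial probabilities summed over all tables for which the Yates-corrected statistic exceeds the 5% critical value. No dropout is applied.

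| g | Treated risk | Difference (points) | Risk ratio | Power, N = 420 | Power, N = 1000 |
|---|---|---|---|---|---|
| 0 | 20.3% | 10.0 | 0.670 | 61.6% | 94.8% |
| 2% | 20.5% | 9.8 | 0.677 | 59.6% | 93.9% |
| 5% | 20.8% | 9.5 | 0.686 | 56.7% | 92.3% |
| 10% | 21.3% | 9.0 | 0.703 | 51.7% | 89.1% |

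**5. What an onset rule recovers.** If pre-randomisation events are dropped, both risks shrink by the same factor. At g = 10% they become 0.303 × 0.9 = 27.3% and 0.203 × 0.9 = 18.3%. The ratio is again 0.67 while the difference stays at 9.0 points. The same exact calculation gives power of 55.4% at 420 and 91.5% at 1000, against 51.7% and 89.1% with those events counted. The rule therefore removes the dilution of the ratio and restores part of the power. It does not restore all of it, because events that fell before randomisation are no longer available to the comparison.

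**The case against.** The strongest reply is that the plan points to early enrolment. Study design says that all patients admitted will be enrolled. Patient's consent places the decision at admission for the very patients most likely to consent late. The natural example, an unconscious patient who wakes on day 4 and then consents, is thus largely answered: that patient's enrolment is decided at admission and consent follows. Late entry would need a patient declined at admission and screened again, and the protocol describes no such route. This part of the reply stands. What remains are conscious patients, for whom no time is given, and patients already in the unit at the start. Nothing suggests that either group is large.

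The 48-hour rule also gives real protection. The window does not open at admission, and for anyone randomised and bathed within 48 hours no earlier infection can count.

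Three stronger readings are tempting and are not supported:
- *The trial is biased towards one arm.* Pre-randomisation events precede allocation and should balance.
- *A patient randomised at 40 hours with onset at 49 hours shows the same fault.* That infection follows randomisation. Whether a minimum exposure should be required is a different question and a matter of preference.
- *A large share of events is affected.* A share such as 20% has no source in the documents and fits poorly with late enrolment being uncommon. The 61.6% starting power at 420 belongs to the sample-size calculation, not to this point.

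Finally, the case report form (attachment 1) and the design figure were not available. The relevant dates may already be collected.

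**Conclusion.** The point holds as a minor one. As written, the protocol counts a pre-randomisation infection for any patient randomised more than 48 hours after admission, and nothing in it prevents such randomisation. The consequence is dilution and some loss of power.

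For assumed shares of 2% to 10%, the loss is 2.0 to 9.9 percentage points of power at 420 patients and 0.9 to 5.7 at 1000. It is nil if all patients are randomised within 48 hours. These figures rest on an absolute 10-point reduction, two-sided testing, no dropout, and pre-randomisation events being equally common in both arms. The true share is unknown. Given the wording on enrolment at admission, it probably lies at the lower end or below.

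**What to change.** Amend the rule in Definitions so that an infection counts only if its onset is after randomisation and at least 48 hours after admission to the unit. Confirm that the case report form holds the date and time of admission, randomisation and infection onset, and add any that are missing. These fields also let the number of late-randomised patients be reported.

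A limit on time to randomisation, such as 24 hours, is not needed for this purpose. The onset rule removes the pre-randomisation events without excluding anyone, and a 24-hour limit would make the onset rule redundant.

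The cost is one sentence and at most a few form fields.

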## **Study design**

Prospective single-blinded randomized case-control study.

Study population: all patients admitted to the Intensive Care Unit (ICU) or to the Post-Cardiosurgical Intensive Care Unit (PC-ICU) of the University Hospital of Perugia will be enrolled.

These patients will be randomized in two arms using a specific software. Patients in the first arm (control arm) will undergo the usual hygiene procedures with standard soap; in the second arm (treatment arm) patients will be bathed with 4% CHG-containing soap (Neoxidina mani 4%), at least 30 ml according to the manufacturer indications (see the attached data sheet). In particular the whole body surface - except for the face - will be i) humidified

[figure not shown]
with water impregnated washcloths, ii) bathed with 4% CHG-impregnated washcloths (at least 30 ml) and, after at least 30 seconds, iii) rinsed with water-impregnated washcloths.

This product is already in use in our hospital to prepare patients before a surgical intervention. We will evaluate and compare the global incidence of sepsis in the two arms and, secondary, incidence of VAP, BSI, CABSI, UTI and CAUTI.

In addition to this, we will collect demographic data of each patients and data about comorbidities, cause of admission and infections occurred during the hospital stay.

This study is single-blind. Physicians that have to collect data, to diagnose infections and to analyse data won't be directly involved in washing procedures and they are not member of the medical staff of ICU and/or TIPOC. Moreover, only nurses that will wash patients by their own hands will know the arm in which the patient is. Both the usual soap and the Neoxidina mani 4% (with chlorhexidine gluconate 4%) have no colour nor other item than can favour their identification.

*Figure 1: Study design*

*Patients enrolment.*

Inclusion criteria: all patients aged  $\geq 18$  years old admitted to ICU or TIPOC.

Exclusion criteria:

- Age  $< 18$  years old;
- patients with burns;
- patients with known allergy to chlorhexidine and/or one of the components of Neoxidina mani 4%;
- patients with toxic epidermal necrolysis o Stevens-Johnson syndrome.
- pregnancy

Data will be collected on specific paper form and, then, analyzed using computerized methods (section "Criteria and data collection methods").

*Relative risk of the procedure and risk/benefit evaluation.*

Neoxidina mani 4% can rarely cause irritation of the exposed surfaces especially after prolonged exposure. To our knowledge, major adverse events due to Neoxidina mani 4% haven't been described till today.

Being randomised to the treatment arm could have a beneficial effect in term of hospital acquired risk reduction.

The aim of the present study is to evaluate if 4% CHG daily bathing in intensive care settings could reduce HAI acquisition rate. As a consequence, considering HAI-associated morbidity mortality and social costs [1-2], benefits appear to be higher than risks.

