### **Data collection.**

We will enrol 420 to 1000 patients in up to one year. Randomisation will be done by a specific software; it will be a simple 1:1 randomisation at patient-level. To evaluate infections we will use data from the routine clinical practice; patients in the two arms will be evaluated in the standard way and without differences between the two arms.

Data will be collected with an ad hoc clinical report form (CRF); data about sex, age, demographic characteristics, comorbidities – evaluated by Charlson comorbidity index – and infections will be collected in the same above mentioned CRF.

These data will be collected and analysed by physicians blinded to the randomisation.

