## **Ethical considerations**

The present study will be conducted to improve the present clinical practise and to reduce the risk of infection during the hospital stay. The proposed strategy appear to be promising to reach the declared aims and almost adverse event free for patients. The present study will be conducted in agreement with the declaration of Helsinki.

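### The protocol names skin irritation as the product's risk, but describes no skin or allergic reaction outcome, data item or analysis, so the trial as described can inform only the benefit side.

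*Combined protocol and SAP*

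**What the plan says.** All references are to the combined protocol and SAP.

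**On risk.** Study design, under the sub-heading on relative risk and risk/benefit evaluation, states that the product "can rarely cause irritation of the exposed surfaces especially after prolonged exposure". It continues: "To our knowledge, major adverse events due to Neoxidina mani 4% haven't been described till today". It concludes that "benefits appear to be higher than risks". Ethical considerations describes the strategy as "almost adverse event free for patients". No reaction rate is given anywhere.

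**On prior experience.** Study design states: "This product is already in use in our hospital to prepare patients before a surgical intervention".

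**On what is measured.**
- The main aim is the effect of daily bathing "on the incidence of HAI in 2 intensive care units". The secondary aim lists specific infections only.
- Study design compares sepsis, VAP, BSI, CLABSI, UTI and CAUTI between arms. The data it lists are demographics, comorbidities, cause of admission and infections.
- Data collection describes a CRF holding "data about sex, age, demographic characteristics, comorbidities" (by Charlson index) and infections.
- Data analysis gives descriptive summaries and two-group tests, with no safety analysis.
- Definitions and methods says, more broadly, that clinical data will also go on the CRF (attachment 1).

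**On mitigation.** Known allergy to the product, burns, toxic epidermal necrolysis and Stevens-Johnson syndrome are exclusions. The face is not washed with the product, and the soap is rinsed off with water.

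**The concern.** The protocol acknowledges a specific, observable harm and makes two reassuring statements about safety, but describes no means of observing that harm in the trial. If the plan is carried out as described, a result favouring the treated arm would come with an infection estimate and nothing on skin or allergic reactions. Anyone weighing adoption would have to rely on the prior knowledge that the protocol already cites.

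That knowledge carries over imperfectly. The experience cited at the hospital is washing before surgery, whereas the trial washes nearly the whole body every day in intensive care. In addition, Sample Size and Patient's consent allow enrolment of patients with altered mentation who consent only on recovery. While they cannot communicate, spontaneous complaint is a weak way of detecting irritation.

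**Working it through.** The protocol states no figure on this point, so there is none to reproduce. The check has two parts.

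**1. Is the named risk covered anywhere?**

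| Section | Content | Skin, allergy or adverse-event item? |
|---|---|---|
| Main aim | HAI incidence | No |
| Secondary aim | VAP, BSI, CLABSI, UTI, CAUTI | No |
| Definitions and methods | Demographic and clinical data on the CRF (attachment not available) | None named |
| Study design, comparisons | Sepsis and specific infections | No |
| Study design, data listed | Demographics, comorbidities, cause of admission, infections | No |
| Study design, exclusions | Already known allergy, some skin conditions | Entry criterion only |
| Data analysis | Descriptive summaries, two-group tests | No |
| Data collection | Sex, age, demographics, Charlson index, infections | No |

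Two separate lists of the data omit the item, and no comparison or analysis uses one.

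**2. What precision would be attainable if it were recorded?**

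Inputs: 420 to 1000 patients (Sample Size, Data collection) with simple 1:1 randomisation (Data collection). The treated arm is therefore about 420/2 = 210 to 1000/2 = 500 patients.

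With zero events among n patients, the exact binomial upper limit is 1 − 0.025^(1/n) for a two-sided 95% interval and 1 − 0.05^(1/n) for a one-sided 95% limit.

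- n = 210, two-sided: 1 − 0.025^(1/210) = 0.0174, about 1.7%.
- n = 210, one-sided: 1 − 0.05^(1/210) = 0.0142, about 1.4%.
- n = 500, two-sided: 1 − 0.025^(1/500) = 0.0074, about 0.7%.
- n = 500, one-sided: 1 − 0.05^(1/500) = 0.0060, about 0.6%.

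Taking the protocol's 8% dropout off the smaller arm leaves 210 × 0.92 ≈ 193 patients, and the two-sided limit becomes 1 − 0.025^(1/193) = 0.0189, about 1.9%.

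The chance of seeing at least one case at true rate r is 1 − (1 − r)^n. The rates below are assumptions, because the protocol says only that irritation is rare.

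| Assumed r | n = 210 | n = 500 |
|---|---|---|
| 0.1% | 19% | 39% |
| 1% | 88% | 99% |
| 5% | >99% | >99% |

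Even the smallest planned trial would probably show a reaction occurring in 1 patient in 100. A rate of 1 in 1000 would more likely than not be missed even with 500 treated patients.

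**The case against.** **The risk/benefit sentence is not a trial conclusion.** A reader might infer that the trial fails to support a claim it sets out to prove. The documents do not support that. The sentence is an ethical judgement made in advance, from prior knowledge of the product and the burden of HAI, and the stated aims concern infections only. What stands is narrower: the trial's described data bear on one side of that judgement.

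**The CRF may contain the item.** A reader might infer that reactions will certainly go unmeasured. This cannot be shown: the attachment was not available, the reference to clinical data is broad, and neither data list claims to be exhaustive. But even if the field exists, no outcome or analysis in the protocol uses it.

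**Daily bathing need not be prolonged exposure.** A reader might equate the two. The protocol does not define the term or make that link, and the soap is rinsed off. Conversely, it gives a minimum contact time but no maximum, and the washing is repeated daily. The text settles the matter neither way, so the point does not rest on it.

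**Mitigation exists and the harm is described as rare.** The exclusions and rinsing reduce the risk, and this properly lowers the urgency. They do not measure what remains.

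**Ascertainment would be unblinded.** This objection stands. The nurses who wash the patients know the arm, so their recording of irritation may be biased. A separate sheet protects the infection assessors but not the safety comparison.

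**Conclusion.** The point holds in a limited form. The protocol identifies irritation as the product's risk, and no described aim, comparison, data item or analysis covers skin or allergic reactions. The validity of the infection comparisons is not affected. As described, the trial will supply evidence on benefit and none on this risk.

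The size of any missed harm cannot be stated. The upper limits of about 1.7% (210 treated) and 0.7% (500 treated) show the precision on offer with no events, not an estimate of harm. They assume an equal split, follow-up of every treated patient and complete recording. The finding also assumes that the unavailable CRF does not change the picture. If the field is already there, what remains is its absence from the protocol text and analysis. This is a worthwhile, inexpensive improvement rather than a defect that threatens the main result.

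**What to change.** - **Study design and Data collection:** add, for both arms, skin or allergic reaction (yes/no, onset date, severity) and whether bathing with the assigned soap was stopped. Record these on a sheet separate from the infection form, so that the infection assessors do not see them.
- **Data analysis:** add a table of these items by arm with exact 95% confidence intervals, and state that they were recorded by staff who knew the allocation.
- **If the CRF already has the field:** name it in the protocol, keep it apart from the infection form, and add the table.

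The cost is a few fields and one table, completed by nurses already at the bedside. No change to the soap, the bathing procedure or the infection analyses is involved. The remaining drawback is possible reporting bias in the between-arm comparison of reactions, which should be disclosed alongside the table.
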